13.9 Ineligible

A patient is deemed *ineligible* if after enrollment, it is determined that at the time of screening, the patient did not satisfy each and every eligibility criterion for study entry. If the patient received treatment, the patient may continue treatment at the discretion of the physician as long as there are not safety concerns. The patient will continue in the Active Monitoring/Treatment phase of the study, as per section 4.0 of the protocol.

If the patient never received treatment, on-study material must be submitted. Survival Follow-up will be required per Section 4.0 of the protocol.

13.10 Major violation

A patient is deemed a *major violation*, if protocol requirements regarding treatment in cycle 1 of the initial therapy are severely violated that evaluability for primary end point is questionable. If the patient received treatment, the patient may continue treatment at the discretion of the physician as long as there are not safety concerns. The patient will continue in the Active Monitoring/Treatment phase of the study, as per section 4.0 of the protocol.

13.11 Cancel

A patient is deemed a *cancel* if he/she is removed from the study for any reason before any study treatment is given. On-study material and the End of Active Treatment/Cancel Notification Form must be submitted. No further data submission is necessary.

OR

For intent to treat trials, use this wording (consult stats) A patient is deemed a *cancel* if he/she is removed from the study for any reason before any study treatment is given. On-study material and the End of Active Treatment/Cancel Notification Form must be submitted. The patient will go directly to the survival follow-up of the study, and survival follow-up will be required per Section 4.0 of the protocol.

14.0 Body Fluid Biospecimens

Please refer to the companion laboratory companion manual for details on collection/processing/kits.

15.0 Drug Information

IND Exempt. See prescribing information for full information.

15.1 Durvalumab (MEDI4736, IMFINZI™):

15.1.1 **Background:** Durvalumab is a human immunoglobulin (Ig) G1 kappa (IgG1κ) monoclonal antibody (mAb) that blocks the interaction of programmed cell death ligand 1 (PD-L1) (but not programmed cell death ligand-2) with programmed cell death 1 (PD-1) on T-lymphocyte (T-cells) and cluster of differentiation (CD)80 (B7.1) on immune cells (IC) and is engineered to reduce antibody-dependent cell-mediated cytotoxicity (ADCC).

15.1.2 **Formulation:** Durvalumab will be supplied by AstraZeneca as a 500-mg vial solution for infusion after dilution. The solution contains 50 mg/mL durvalumab, 26 mM histidine/histidine hydrochloride, 275 mM trehalose dihydrate, and 0.02% weight/volume (w/v) polysorbate 80; it has a pH of 6.0 and density of 1.054 g/mL. The nominal fill volume is 10.0 mL. Investigational product vials are stored at 2°C to 8°C (36°F to 46°F) and must not be frozen. Drug product should be kept in original packaging until use to prevent prolonged light exposure.

15.1.3 **Preparation and storage:** Withdraw desired volume from vial and dilute in either 0.9% sodium chloride or 5% Dextrose in Water to a final concentration of 1 to 15 mg/mL. Total time from needle puncture of the durvalumab vial to the start of administration should not exceed 24 hours at 2°C to 8°C (36°F to 46°F) or 4 hours at room temperature. Infusion solution must be allowed to equilibrate to room temperature prior to commencement of administration.

15.1.4 **Administration:** Durvalumab is delivered through an IV administration set with a 0.2- or 0.22-micron filter. The standard infusion time is 1 hour. Do not co-administer other drugs through the same infusion line. Flush the IV line with a volume of IV diluent equal to the priming volume of the infusion set used after the contents of the IV bag are fully administered.

15.1.5 **Pharmacokinetic information:**

- **Volume of Distribution:** The mean volume of distribution at steady state was 5.6 liters
- **Half-life elimination:** The mean terminal half-life at steady state was approximately 18 days.
- **Excretion:** Mean steady state clearance was 8.2 mL/hr.

15.16 **Potential Drug Interactions:** Durvalumab is an immunoglobulin; therefore, no formal pharmacokinetic drug-drug interaction studies have been conducted.

15.17 **Known potential toxicities:**

- **Very common, > 10%:** Fatigue, cough, decreased appetite, dyspnea, nausea, constipation, diarrhea, pyrexia, back pain, anemia, vomiting, pruritus, arthralgia, headache, asthenia, peripheral edema, rash.
- **Common, 1% - 10%:** Abdominal pain, hypothyroidism, insomnia, urinary tract infection, myalgia, dizziness, AST and ALT increased, musculoskeletal pain, upper respiratory tract infection, pneumonia, weight decreased, pain in extremity, hyponatremia, productive cough, dehydration, hyperthyroidism, musculoskeletal chest pain, radiation pneumonitis, hypokalemia, GGT increased, blood alkaline phosphatase increased.
- **Rare, <1% (Limited to important or life-threatening):** Pulmonary embolism, respiratory failure, COPD, hemoptysis, atrial fibrillation, pericardial effusion.

15.18 **Procurement:** Durvalumab will be provided free of charge to study participants from AstraZeneca.

15.2 Nursing Guidelines

- 15.2.1 Anti PD-L1 side effects vary greatly from those of traditional chemotherapy and can vary in severity from mild to life threatening. Instruct patients to report any side effects to the study team immediately. Side effects may be immediate or delayed up to months after discontinuation of therapy. Most side effects are reversible with prompt intervention of corticosteroids.
- 15.2.2 Diarrhea can be common and can be very severe, leading to colonic perforation. Instruct patients to report ANY increase in the number of stools and/or change in baseline, blood in the stool, abdominal pain to the study team immediately.
- 15.2.3 Rash/pruritis/dermatitis is seen. Patients should report any rash to the study team. Treat per section 8.0 and monitor for effectiveness.
- 15.2.4 Monitor LFT's closely as elevations in these levels could indicate early onset autoimmune hepatitis. Patients should also be instructed to report any jaundice, or right upper quadrant pain to the study team immediately.
- 15.2.5 Pneumonitis can be seen and may be mild (only seen on imaging) to severe. Patients should be instructed to report any SOB, dyspnea, cough, chest pain, etc. to the study team immediately. Patients reporting these symptoms should have a pulse ox checked and consider immediate imaging per the treating MD.
- 15.2.6 Endocrinopathies (including hypopituitarism, hypothyroidism, hypophysitis, and adrenal insufficiency) are a concern given the mechanism of action of this agent. Patients may present only with the vague sense of fatigue and "not feeling well". Additional symptoms may be that of nausea, sweating and decreased activity tolerance. Instruct patients to report these signs or symptoms immediately and obtain appropriate labs as ordered by MD.
- 15.2.7 Pancreatitis is possible with anti PD-L1 therapy based on mechanism of action. Instruct patients to report abdominal pain, nausea and vomiting to the study team.
- 15.2.8 Patients who are started on steroid therapy for any side effects of anti PD-L1 toxicity should be instructed to take the steroids as ordered, and not to discontinue abruptly as symptoms may return and be severe. Patients may be on steroid therapy for weeks. Instruct patients to report any increase or change in side effects with any dosage decrease as patients may need a slower taper.

16.0 Device Information

This medical device is utilized under an investigator-sponsored Investigational Device Exemption (IDE), [name], M.D. IDE Sponsor. The use and prescription of TheraSpheres is not under the HDE approval.

16.1 TheraSpheres [Yttrium-90 Glass Microspheres)

- 16.1.1. **Background:** TheraSpheres is indicated only for radiation treatment or as a neoadjuvant to surgery or transplantation in patients with unresectable carcinoma (HCC) who can have placement of appropriately positioned hepatic arterial catheters and is approved for this indication under Humanitarian Device Exemption H980006.
- 16.1.2. **Regulatory Status.** Use of this device is limited to the subjects meeting explicit protocol criteria under the investigational device exemption (IDE XXXXXX, [name] sponsor-investigator).
- 16.1.3. **Labeling.** The investigational device and/or package will have a label stating it is for investigational use only and limited by Federal law to investigational use, as well as all other required contents per 21CFR§812.5(a)

16.1.4 **Records.** Shipment, disposition, and destruction of the device must be documented by research personnel authorized per the delegation log. Accountability and receipt records documenting the device life-cycle must be used per 21CFR§812.40.

16.1.5 **Prescription.** Individuals authorized to prescribe must be an authorized user (10CFR§35) and have been delegated the authority from the IDE sponsor.

16.1.6 **Administration.** TheraSpheres will be planned and administered per the approved package insert as well as following currently recommended guidelines: Sangro et al (2017), Lau et al (2012), Venkatanarsimha et al (2017), as well as the EANM procedure guideline for intra-arterial radioactive compounds (Giammarile et al 2011). Per package insert, targeted administrations will fall within recommended values of 80 Gy to 150 Gy per lobe of liver in order to preventing radioembolization induced liver disease (REILD). Required activity at the time of administration and actual dose delivered to the liver may be respectively calculated as

$$\text{Activity Required (GBq)} = \frac{[\text{Desired Dose (Gy)}][\text{Target Liver Mass (kg)}]}{50}$$

$$\text{Dose (Gy)} = \frac{50[\text{Injected Activity (GBq)}][1 - F]}{\text{Affected Liver Mass (kg)}}$$

, where F is the lung shunting fraction measured during the Tc-99m labelled MAA eligibility mapping. Additional eligibility criteria will include the absence of shunting to bowel along the GI tract as well as a lung shunting fraction (F) <15% or estimated lung doses <30 Gy for a single Y90-RE administration and a cumulative total of <50 Gy from multiple administrations. As noted earlier, from a safety perspective since we need to know about the shunting to other organs prior to the Y90-RE, the mapping can be done during the screening or even prior to considerations for this study if already performed within 12 months of intended Y90-RE, it would not need to be repeated unless as per interventional radiology.

16.1.7 **Drug interactions.** External beam radiation is known to interact with immunotherapy, often resulting in heightened immune responses. (Wang et al, 2018, PMID 29556198).

16.1.8 **Radiation observation window.** Due to the long-term side effects of radiation therapy, it is recommended subjects be followed for a minimum of 2 years post-radiation.

16.1.9 **Procurement.** Investigational device will be ordered by the IDE sponsor or delegate. Upon receipt, it will be labelled as per 21CFR§812.5(a) and secured. Subject will be billed for the research device as allowed under 42CFR§405 Subpart B upon approval by the appropriate CMS contractor.

17.0 Statistical Considerations and Methodology

17.1 Study Design

This is a single arm phase I study designed to determine the maximally tolerated dose (MTD) and toxicity profile of Yttrium-90 radioembolization combined with immunotherapy in the treatment of liver-predominant, metastatic colorectal cancer using the accelerated titration design.

Once the MTD is reached, if total accrual is less than 18, additional patients will be enrolled in an expansion cohort to reach full accrual of 18 patients.

17.2 MTD Definition and Determination

For this protocol, the patient must return to clinic for evaluation at least every **14** days +/- 5 days. Patients will be treated and observed for a minimum of **8** weeks post-Y90-RE before new patients are treated. Doses will not be escalated in any individual patient.

MTD Definition: The MTD will be defined as the highest dose level for which at most 1 out of 6 patients experience a dose-limiting toxicity (DLT). A total of 6 patients treated at the MTD will be sufficient to identify common toxicities at the MTD. For instance, those toxicities with an incidence of at least 25% will be observed with a probability of at least 82% (1-(1-0.25)⁶).

Refer to Section **7.42** for definition of dose-limiting toxicity (DLT).

MTD Determination:

This study will utilize an accelerated titration design. The dose levels to which patients will be assigned in sequential cohorts are listed in the table below.

		Immunotherapy (Durvalumab) Administrations					
		Pre-Y90 doses		Post-Y90 doses		Number of Administration of Durvalumab	
Dose level	Week -2	Week 0	Y90-Radio-embolization	Week 2	Week 4	Week 6	
					X		1
-2					X		2
-1							2
1 (start)	X	X					3
2	X	X		X			4
3	X	X		X	X		5
4	X	X		X	X	X	

In the first phase, a single patient will be treated per dose level until the first DLT is recorded. Once the first DLT is recorded, two additional patients are treated at the same dose level and the trial reverts to a standard 3+3 design in the second phase. At which time, decisions on when and how to dose escalate are described below.

Number of patients with DLT at a given dose level	Decision Rule
0 out of 3	Enter 3 patients at the next higher dose level
1 out of 3	Enter up to 3 additional patients at the same dose level. 
 • If 0 of these 3 patients experience DLT, proceed to the next dose level. • If 1 or more of these 3 patients experience DLT, then dose

	escalation is stopped, and this dose is declared the maximally administered dose. Three (3) additional patients will be entered at the next lowest dose level if only 3 patients were treated previously at that dose.
≥2 out of 3	Dose escalation will be stopped. This dose level will be declared the maximally administered dose. Three (3) additional patients will be entered at the next lowest dose level if only 3 patients were treated previously at that dose.

Up to 6 patients will be treated at each dose level. If DLT meets the stopping boundaries set by the above dose algorithm at dose level 1 (for example, more than 1 out of 3 or more than 1 out of 6 patients), the next cohort of 3 patients will be entered at the dose level of -1. If dose level -1 meets the stopping boundaries, the next cohort of 3 patients will be entered at dose level -2.

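### For levels reached by de-escalation the 3+3 rules contradict each other: 0 of 3 DLTs at level -1 points back to the stopped level 1, and if that return is refused no rule brings level -1 to the six patients in the MTD definition.

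*Combined protocol and SAP*

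**What the plan says.** The rules are in Section 17.2 of the combined protocol and SAP, and the table and de-escalation text also appear in Section 1.4.6.

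- After 0 of 3 DLTs: "Enter 3 patients at the next higher dose level". After 1 of 3 and an expansion to six: "If 0 of these 3 patients experience DLT, proceed to the next dose level". Neither instruction depends on how the level was reached.
- After 2 or more of 3: "Dose escalation will be stopped. This dose level will be declared the maximally administered dose". One or more DLTs in the second three has the same effect. Both stopping outcomes carry a back-fill clause: three "additional patients will be entered at the next lowest dose level if only 3 patients were treated previously at that dose".
- Below the table, if level 1 meets the stopping boundary, "the next cohort of 3 patients will be entered at the dose level of -1". Then: "If dose level -1 meets the stopping boundaries, the next cohort of 3 patients will be entered at dose level -2".
- The cap: "Up to 6 patients will be treated at each dose level".
- The MTD is the "highest dose level for which at most 1 out of 6 patients experience a dose-limiting toxicity". Section 17.2 adds that six patients there suffice to show common toxicities, with at least 82% probability for a toxicity of 25% incidence.
- Section 1.4.6 adds a fallback: without an MTD, the expansion cohort follows the cohort 4 schedule, which is the highest level.

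**The concern.** The de-escalation text covers one result at level -1, a stop, which leads to level -2. For a good result the reader has only the table, and its two favorable instructions point upward. From level -1 that is level 1, which has just been declared the maximally administered dose. From level -2 it is level -1, which has also been stopped.

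Two different things are at stake, depending on how the conflict is resolved. If the row is followed, three patients are treated at a level that has already failed and cannot become the MTD. If it is not followed, the best possible result at level -1 leaves three patients there, the six-patient definition is not met, and the fallback in 1.4.6 literally sends the remaining patients to the highest level after the lowest escalation level was stopped.

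**Working it through.** **The plan's own figure.** The probability of seeing at least once a toxicity of 25% incidence in six patients is 1 - 0.75^6 = 0.822, which reproduces the stated 82%. With three patients it is 1 - 0.75^3 = 0.578. The one-sided 95% upper limit for the DLT rate, 1 - 0.05^(1/n), is 63.2% after 0/3 and 39.3% after 0/6.

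**Tracing the rules after level 1 stops and level -1 shows 0/3.**

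1. *Level 1 stopped with three patients (2 or more of 3).* The cap leaves three places, so the 0/3 row can be carried out. Level 1 already has at least 2 DLTs and cannot finish with at most 1 in 6. The three returned patients would carry 3p expected DLTs: 0.39, 0.75 and 0.99 at p = 13%, 25% and 33%. Counted cumulatively, level 1 again meets the boundary, the text below the table sends three more to level -1, and level -1 does reach six.
2. *Level 1 stopped with six patients (1 of 3, then 1 or more of 3).* The cap bars a return, and no other rule adds patients at level -1.
3. *Either case, with the halt to escalation overriding the 0/3 row.* Level -1 again stays at three. The back-fill clause does not help: it acts when the level above stops and requires three patients already at the lower level, and level -1 then has none.

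A result of 1/3 then 0/3 at level -1 is different. It is 1 of 6 and meets the MTD definition, although the table still points upward.

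**How often.** The documents give no DLT rates, so 13%, 25% and 33% are assumptions. The lowest borrows, for scale only, the frequency of grade 3 or 4 hyperbilirubinemia in the retrospective glass-microsphere series in Section 1.2.2. Let p be the rate at level 1 and q the rate at level -1. Level 1 starts with one patient, and only stops that begin with a DLT in that patient are counted.

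- A: level 1 stops with three patients = p[1 - (1-p)^2]
- B: level 1 stops at all = p[1 - (1-p)^5]
- C: 0/3 at level -1 = (1-q)^3
- D: level -1 clears (0/3, or 1/3 then 0/3) = (1-q)^3 + 3q(1-q)^2 × (1-q)^3

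| p, q | A | B | C | D | Return that fits the cap, A×D | Level 1 stopped, then 0/3, B×C |
|---|---|---|---|---|---|---|
| 13%, 13% | 0.032 | 0.065 | 0.659 | 0.853 | 2.7% | 4.3% |
| 25%, 25% | 0.109 | 0.191 | 0.422 | 0.600 | 6.6% | 8.0% |
| 33%, 33% | 0.182 | 0.285 | 0.301 | 0.434 | 7.9% | 8.6% |
| 33%, 13% | 0.182 | 0.285 | 0.659 | 0.853 | 15.5% | 18.8% |

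The last two columns overlap and must not be added. In the part of B×C where level 1 stopped with six patients, (B-A)×C, level -1 is left at three on either reading: 2.2%, 3.4%, 3.1% and 6.8% in the four rows.

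**Patients left for expansion.** With level -1 left at three, 3+3 = 6 or 6+3 = 9 patients have been used, so 12 or 9 of the 18 would fall under the fallback.

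**The case against.** The plan does contain de-escalation rules: the sentences below the table and the back-fill clause. The table is introduced as governing escalation, it says escalation stops once a level is declared the maximally administered dose, and the design is called a standard 3+3. An experienced team would probably not return to level 1. Safeguards exist too: dose level is checked with the coordinator or investigator before entry (Section 3.0), the Study Chair is told of any DLT (7.4.1.2), DLTs are reported within one business day (10.5.5), and patients are observed for eight weeks before new ones are treated (17.2). Section 17.3 expects no DLTs, and the branch needs one in the first patient at level 1.

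Most of this stands, and it limits the point. A reader might infer that the plan has no de-escalation provision, or that it plainly orders patients back to level 1. Neither is supported: provisions exist, and the return is one side of a contradiction. A reader might also infer that both harms occur together. They do not, because a return followed by a second stop brings level -1 to six. Multiplying every level 1 stop by every clearance of level -1 (B×D) gives 5.6%, 11.4% and 12.4%, but this overstates both harms. It includes stops at six patients, where the cap bars a return, and results of 1/6, which already meet the MTD definition.

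What the objection does not supply is the missing rule. If the halt to escalation prevails, nothing says how 0/3 at level -1 becomes six patients. Declaring level -1 the MTD and filling it through the expansion is circular, because the expansion at that level presupposes an MTD. De-escalation rules are also needed precisely when the expectation of no DLTs has failed.

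**Conclusion.** The point holds as a contradiction in a stated decision rule, not as an unambiguous instruction to re-treat at a stopped level. On one reading, patients return to a level that can no longer qualify. On the other, and always when level 1 stopped with six patients, 0/3 at level -1 yields no MTD under the written definition, the plan's 82% detection probability falls to 58%, and the literal fallback is the cohort 4 scheme. The same gap exists at level -2 relative to level -1.

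With equal assumed rates of 13% to 33%, a return that fits the cap has probability 2.7% to 7.9%, and a stopped level 1 followed by 0/3 at level -1 has 4.3% to 8.6%. If the rate is 33% at level 1 and 13% at level -1, these are about 16% and 19%. All rest on assumed DLT rates and independent patients. The contradiction itself rests on the text alone.

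**What to change.** Reconcile the decision table, the de-escalation text and the fallback, in Sections 1.4.6 and 17.2 alike, so that:

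- both upward instructions (after 0/3, and after 1/3 then 0/3) agree with the statement that escalation has stopped, for levels reached by de-escalation;
- the text states how a 0/3 result at level -1 or -2 relates to the six-patient MTD definition;
- the provision in 1.4.6 for the case without an MTD is consistent with level 1 having been stopped.

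Which rule applies is for the sponsor to decide. The cost is a few lines in two sections. Even six patients at each of levels 1, -1 and -2 would be 6+6+6 = 18, within the planned accrual.

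### The escalation rules in 17.2 do not deliver the plan's own MTD definition (at most 1 DLT in 6) or its count of 9 patients

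*Combined protocol and SAP*

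**What the plan says.** Section 17.2 states the definition: "The MTD will be defined as the highest dose level for which at most 1 out of 6 patients experience a dose-limiting toxicity (DLT"). It adds: "A total of 6 patients treated at the MTD will be sufficient to identify common toxicities at the MTD", and supports this with an 82% chance of seeing a toxicity of 25% incidence. Sections 1.4.6 and 17.3 both put the number needed to establish the highest level as the MTD at 9 evaluable patients, and 17.3 says that DLTs are not expected.

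The operating rules, in 17.2 and repeated in 1.4.6, are these:

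- Accelerated phase: "In the first phase, a single patient will be treated per dose level until the first DLT is recorded". After the first DLT, two more patients join that level and the design becomes 3+3.
- 0 of 3: "Enter 3 patients at the next higher dose level".
- 1 of 3: up to three more at the same level; escalate if none of them has a DLT, otherwise stop.
- On any stop: "Three (3) additional patients will be entered at the next lowest dose level if only 3 patients were treated previously at that dose".
- Ceiling: "Up to 6 patients will be treated at each dose level".
- Below level 1: cohorts of three at level -1, and then "If dose level -1 meets the stopping boundaries, the next cohort of 3 patients will be entered at dose level -2".

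Sections 1.4.6, 1.4.7, 17.1 and 17.3 place the expansion cohort at the MTD, to a total of 18. Section 1.4.6 also says that if no MTD is determined, the expansion uses the cohort 4 scheme. Footnote 17 of the test schedule (4.1) labels the five-dose schedule as the dose expansion cohort.

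**The concern.** The definition needs six patients at the declared level, but the rules reach six on only some paths. The backfill clause is standard 3+3 wording and assumes that every lower level was cleared with three patients. Here the accelerated phase clears levels with one. The 0-of-3 row points to a higher level, which does not exist above level 4.

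Section 17.1 names the MTD as the aim of the design, and the recommended phase II dose is a secondary goal. What is lost is the decision point: no stated step applies the 1-in-6 criterion to level 4 before the expansion opens.

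The fallback in 1.4.6 makes this worse. Read literally, it sends the expansion to the cohort 4 scheme after a single patient at level 4. It also does so after a stop for DLTs at level 2, 3 or 4 with one patient at the level below, because no level then meets the definition.

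**Working it through.** **The plan's own figures.** 1 − 0.75^6 = 0.822, so the 82% is right for six patients. The 9 is reproduced as 1+1+1+6, with level 4 filled to six.

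**The table on the no-DLT path.** One patient at each of four levels gives 4, with one at level 4. No later row applies.

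**The backfill.** A level cleared in the accelerated phase holds one patient, so the condition of exactly three is not met. Reading it as three or fewer gives 1 + 3 = 4, still not six.

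**How often this happens.** The documents give no DLT rates, so I assume a flat rate p of 5/10/20% at every level. I enumerate the written rules exactly, with levels -1 and -2 included and the 18-patient cap not imposed.

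- Level 4 ends at 0/1: (1−p)^4 = 0.815/0.656/0.410.
- Level 4 ends at 0/3 (enumerated): 0.092/0.105/0.057.
- First DLT at level k (2 to 4), level k then fails, and one patient sits at k−1. Level k passes only if the next five patients are DLT-free, so the probability is the sum over k of (1−p)^(k−1) × p × [1 − (1−p)^5] = 0.031/0.100/0.262. For k = 4 alone it is 0.010/0.030/0.069.
- These three sum to 0.937/0.861/0.729: escalation ends at levels 1–4 with fewer than six at the highest cleared level in 94/86/73% of trials.
- Level -1 or -2 cleared at 0/3 adds 0.010/0.033/0.089.
- The definition is met as written in 5/11/17%. This includes level 4 at 1 of 6 in 4.6/6.9/5.6%; the rest is lower levels at 1 of 6 or backfilled from three to six.

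**With a fill to six and no further step down after a failed fill.** The definition is met in 98/93/79% of trials, and within 18 patients in 97/90/76%. The 20% figures vary by about 0.3 percentage points with how a failed backfill is handled.

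**What is known when the expansion opens (no-DLT path).**

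| | Table alone | Filled to six |
|---|---|---|
| Escalation patients | 4 | 9 |
| At level 4 at that moment | 1 | 6 |
| Expansion places left of 18 | 14 | 9 |
| Chance of having seen a 25% toxicity at level 4 | 1 − 0.75 = 25% | 82% |
| Total at level 4 if the expansion is there | 1 + 14 = 15 | 6 + 9 = 15 |

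By 15 patients the chance is 1 − 0.75^15 = 99% either way.

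**Whether the check can change the decision.** After a DLT-free first patient at level 4, the level fails the definition if at least 2 of the next 5 have a DLT: 1 − (1−p)^5 − 5p(1−p)^4 = 0.023/0.081/0.263.

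**The case against.** The intent is clear. The definition, the sentence on six patients, the ceiling of six and the count of 9 all point to six at the top level, so a team reading the plan as a whole would probably fill level 4. On that view the 5/11/17% measures the table read alone, not how the trial would run. That is fair, and I use the figure only in that sense. But staff follow the table, the ceiling permits six without requiring it, and 1.4.6 gives a different instruction for the very case the table leaves open.

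The table also works on some paths. The 1-of-3 row can bring any level, including level 4, to six, and backfill works where the level below was a 0/3 cohort. Level 4 is declared at exactly 9 patients on one path: the first DLT occurs in the first level 4 patient and the next five have none. Its probability is p(1−p)^8, or 3.3% at p = 5% and 4.3% at 10%.

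The fallback was probably meant for a trial in which no level proved intolerable. Applying it after a stop at level 2 or 3 is a literal reading that sits badly with the rule that escalation has stopped. It carries less weight than the case of level 4 at 0/1, but the text does not exclude it.

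Finally, the missing check does not add exposure: 15 of 18 patients are at level 4 either way. DLT reporting, committee review, the default to 3+3 after any DLT (1.4.6) and the requirement to observe patients for at least 8 "weeks post-Y90-RE before new patients are treated" all remain. If that sentence also governs the expansion, the 14 places would not all fill at once. These are real safeguards, but none of them applies the 1-in-6 criterion at a stated point.

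**Conclusion.** The concern holds and should be corrected before the design is used. The counts 4, 9, 1 and 3 come from the text and need no assumed rate: the rules yield 4 patients where the plan says 9, and one at level 4 where the definition needs six. The percentages rest on flat assumed DLT rates; the shortfall is large at each of the three rates. The loss is of a formal decision point before the expansion. I do not claim that total DLTs in the trial would fall, and I take no view on which level the expansion should use.

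**What to change.** In 17.2 and 1.4.6, replace the backfill condition with one that applies when fewer than six patients were treated at the level, filling it to six. Apply it to any level about to be declared the MTD, including level 4 and levels -1 and -2. State in 17.3 that 9 is the no-DLT count under this rule.

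The sponsor should also:

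- reconcile the fallback in 1.4.6 and the label in footnote 17 of 4.1 with 1.4.7 and 17.1–17.3 on when and at which level the expansion opens, including when escalation has stopped and no level meets the definition;
- state what follows if a filled level fails the definition;
- say whether the second to sixth patients at a level may enrol together under the 8-week sentence in 17.2;
- cross-reference the stopping rules mentioned in 10.5, which may sit in the monitoring plan that 10.0 says is on file.

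**Cost.** Total N stays 18, and so does the immune-response estimate, which 17.3 takes across dose levels. On the no-DLT path there are 9 expansion patients instead of 14. At 5/10/20%:

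| | As written | Fill, no further step down | Fill, with step down after a failed fill |
|---|---|---|---|
| Mean escalation size | 5.4/6.3/7.2 | 9.9/10.5/11.0 | 10.0/10.9/12.3 |
| Escalation exceeds 18 patients | 0.3/1.3/2.1% | 1.4/3.1/3.3% | 1.5/3.8/8.8% |

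If the five fill patients at level 4 enrol together, the expansion opens about 2 + 8 = 10 weeks later. If the 8-week sentence means one at a time, the delay is about 5 × 10 = 50 weeks.
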